Recognizing the inappropriate treatment of ASB to be a problem in acute care, a novel intervention was defined, in which identification and susceptibility results for positive urine culture results were not made available to physicians, unless the physician called the microbiology laboratory.(10) This “modified reporting” was associated with a reduction in the rate of antibiotic treatment of AB from 48% to 12% (number needed to report for benefit = 3) among non-catheterized inpatients, using historical controls.

A randomized, unblinded controlled trial was performed in acute care in St. John's, among patients without indwelling catheters, using the same intervention.(11) Results of positive urine cultures from 110 consecutive inpatients at two urban hospitals were randomised to

standard report or modified report. Specimens randomized to the modified report were reported as follows: "This POSITIVE urine culture may represent asymptomatic bacteriuria or urinary tract infection. If urinary tract infection is suspected clinically, please call the microbiology laboratory for identification and susceptibility results."

Exclusion criteria were age less than 18 years, pregnancy, presence of an indwelling urinary catheter, samples from patients already on antibiotics, neutropenia, or admission to an Intensive Care Unit. Patients were followed for seven days, and physician treatment decisions were observed. 76/110 (69%) of positive urine cultures represented ASB. The proportion of appropriate treatment (UTI treated plus ASB not treated) was higher in the modified arm than in the standard arm (44/55 (80.0%) vs 29/55 (52.7%), absolute difference=-27.3%, RR=0.42, p=0.002, Number needed to report for benefit=3.7).

There were two bacteremias in the modified report group, and one bacteremia in the standard report group, none of which were considered related to the intervention. There were two deaths in the modified report group, and one death in the standard report group, none of which were considered related to the intervention. Based on this trial, the intervention was considered safe over 7 days of followup, and effective to reduce inappropriate treatment, but further study would be required among populations excluded from the trial.

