We propose to repeat the trial using an identical design and intervention, but including only urine collected from long term care facilities (LTCF). The control arm is standard of care. We hypothesize that the modified reporting intervention will also reduce treatment of ASB in the LTCF population, without causing harm.

Objectives

Research Question: Among patients with positive urine cultures collected from LTCF reported by Health Sciences microbiology laboratory, would restricted reporting, as compared to standard reporting, lead to a reduction in the rate of inappropriate antibiotic therapy without an increase in bacteremia or death over 30 days?

Trial design

Randomized controlled trial, 2 parallel groups with equal allocation, superiority analysis.

Methods: Participants, interventions, and outcomes

The proposed study is a randomized trial of two methods of laboratory reporting in which physicians are the main research participants. At the time of positive urine culture results, the specimen will be randomized in the laboratory using computer generated random numbers placed into serially numbered sealed, opaque envelopes, into two equal groups. One group will receive modified reporting, and the other group will receive standard reporting of bacterial identification and susceptibility. Physicians receiving modified reports will have the option to call the laboratory to receive complete results, or not. Complete results will be released by laboratory information system to physicians who call to request them. Physicians will be informed about the study prior to initiation, and debriefed about the study after the results have been collected.

The primary efficacy outcome is proportion of appropriate antibiotic therapy prescribed by physicians, based on published diagnostic criteria for ASB and UTI among catheterized patients. Appropriate therapy is defined as any treatment for UTI, or no treatment for ASB. Inappropriate therapy is defined as no treatment for UTI, or treatment for ASB. The primary safety outcome is rate of bacteremia and death. The study investigators will determine the

diagnosis based on a chart assessment to determine if the patient has UTI, CA-UTI, ASB or CA-ASB.

The definition of UTI in LTCF will be based on 2017 Canadian LTCF surveillance guidelines.(12) For residents without an indwelling catheter, criteria 1 and 2 must be present with no other identified source of infection, OR criteria 2 and 3.

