elderly with high care needs. One centralized microbiology laboratory performs all testing for the city.

Inclusion and exclusion criteria for participants

Consecutive positive urine cultures collected from patients admitted to LTCF will be included. All methods of urine collection will be included (midstream, in-and-out catheterization, indwelling catheter). Exclusion criteria will be urine cultures not collected from LTCF patients, pregnancy, antibiotic treatment at the time of collection, and patients known to have blood neutrophils <1.0 within 7 days.

Interventions

The modified report states “This POSITIVE urine culture may represent asymptomatic bacteriuria or urinary tract infection. If urinary tract infection is suspected clinically, please call the microbiology laboratory at [name] between 0900 to 2300, or the microbiology technologist on-call at [name] at night, for identification and susceptibility results.” The standard report provides bacterial count, bacterial identification and bacterial susceptibility results.

The report is provided to the physician approximately 24 hours after receipt of the specimen, when cultures have been examined after overnight incubation. The intervention is a single report, so it is not possible to discontinue the intervention, or change allocation during the trial. There will no other influence on concomitant care or treatment.

Outcomes

Primary efficacy outcome:

Proportion of appropriate antibiotic therapy prescribed by physicians. Appropriateness is determined by investigators based on chart review, based on diagnosis of UTI or ASB. Appropriateness is determined within two days from positive urine culture.

Secondary efficacy outcomes:

Proportion of calls from physicians requesting complete report

Primary safety outcomes:

Mortality rate over thirty days from positive urine culture.

Bacteremia rate over thirty days from positive urine culture.

Adverse event rate over seven days from positive urine culture.

Participant timeline

TIMEPOINT	STUDY PERIOD				
	Enrolment	Allocation	Post-allocation		
	Day -1	Day 0	Day 2	Day 7	Day 30
ENROLMENT:					
Eligibility screen	Urine specimen received at microbiology laboratory	Urine culture result reported to physician	Physician treatment decision made	Safety assessment	Safety assessment
Allocation	X				
INTERVENTIONS:					
Reporting		X			
ASSESSMENTS:					
Appropriateness			X		
Adverse Events			X	X	X
Bacteremia			X	X	X
Mortality			X	X	X

Sample size

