In the previous trial of the same intervention, modified reporting increased the appropriateness of treatment from 29/55 (52.7%) to 44/55 (80.0%) ($p=0.002$), for an absolute difference of +23%.(11) Accepting a risk of type 1 error of five percent, and a risk of type 2 error of twenty percent, the study will require $2N=90$ patients. To account for missing data, recruitment will be increased to 100 patients.

The microbiology laboratory receives 130 urine specimens per day, with 30 percent reported as significant growth (40 specimens per day). Ten percent are submitted from LTCF (4 positive specimens per day). In the previous trial, approximately 40% of eligible specimens were excluded based on exclusion criteria. Recruitment of 100 specimens will require approximately 40-60 days.

The statistical test to be used is a comparison of proportions between two groups (T test, two-sided analysis). Because true diagnosis may be biased by lack of access to clinical information, an intention to treat analysis including all patients randomized will be performed.

Recruitment

Every urine specimen received for culture during the study period will be assessed for inclusion.

Allocation:

Sequence generation

Randomization sequence will be generated without blocking or stratification (Research Randomizer 4.0)(13).

Allocation concealment

Reporting assignments will be placed into serially numbered, sealed, opaque envelopes.

Implementation

Allocation sequence will be generated by investigators. Investigators will enroll specimens and assign specimens to reporting interventions.

Blinding

Trial participants (physicians) will not be blinded to the intervention because the laboratory report will reveal the intervention. Investigators will be blinded to assignment. Data analyst will not be blinded to assignment.

Data collection methods

After randomization and reporting, a physician investigator will assess inpatients for the true diagnosis of UTI or ASB at two days after reporting. Health records will be accessed including demographics, symptoms, treatment decisions and outcomes.

If patients are discharged from hospital before thirty days, primary care physicians will be contacted by phone for additional clinical information. If patients die before thirty days, available data will be analyzed.

Frequency of physician calls requesting complete reporting will be recorded.

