Urine culture is reported according to laboratory protocol by licenced medical laboratory technologists, in categories of significant growth, non-significant growth, and no growth, based on quantity of growth and number of bacterial types detected. Antimicrobial susceptibility is reported according to laboratory protocol, including selected first and second-line antibiotics, as susceptible, intermediate or resistant. Drug cost and dosage suggestion are provided.

Data collection form attached.

Data management

Data collection will use a paper case report form, and entered into a trial database by a graduate student. Variables will be coded appropriately. The dataset will be protected using a

password and stored on a laptop computer during data entry. After data entry is completed, data integrity will be reviewed by a second investigator, and then the dataset will be locked for analysis.

Statistical methods

All specimens randomised and reported will be included in the Intention-to-treat (ITT) analysis. Specimens inappropriately included will be excluded from the Per-protocol (PP) analysis. The proportion of appropriate treatment will be compared using two-sided Pearson chi squared test (SPSS 23.0, IBM, USA). Adjusted analysis may be performed if appropriate. A subgroup defined as specimens in which physicians requested complete reporting will be analysed for appropriateness, compared to the standard reporting arm. Missing data will not be imputed.

Data monitoring

A data monitoring committee will not be used, as a single investigator will assume responsibility for data quality. A single interim analysis at approximately 50% recruitment will be performed, and the study stopped if the primary outcome achieves statistical significance.

Harms

Serious adverse events will be reported to the ethics committee within 24 hours. Adverse events will be collected by the investigators at day 2, day 7 and day 30. Patients with adverse events will be provided care in hospital.

Auditing

There will not be auditing of trial conduct during or after the trial.

Research ethics approval

The protocol will be submitted to the Provincial Health Research Ethics Board.

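### Appropriateness is scored only at day 2 and no outcome captures later antibiotic starts, so the trial cannot tell avoided treatment from delayed treatment

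*Combined protocol and SAP*

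**What the plan says.** The Methods section defines success without a time limit: "Appropriate therapy is defined as any treatment for UTI, or no treatment for ASB". The Outcomes section adds the limit: "Appropriateness is determined within two days from positive urine culture". Data collection methods agrees on timing, stating that "a physician investigator will assess inpatients for the true diagnosis of UTI or ASB at two days after reporting". One section counts from the positive culture and the other from reporting; nothing below depends on that difference.

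The Participant timeline marks appropriateness at day 2 only. Days 7 and 30 are labelled as safety assessments and cover adverse events, bacteremia and mortality. Harms says "Adverse events will be collected by the investigators at day 2, day 7 and day 30". The only secondary efficacy outcome is the proportion of physician calls for the complete report.

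The two arms receive different information at reporting. Under Interventions, "The report is provided to the physician approximately 24 hours after receipt of the specimen", and "The standard report provides bacterial count, bacterial identification and bacterial susceptibility results". For the other arm, Methods says "Physicians receiving modified reports will have the option to call the laboratory to receive complete results, or not".

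**The concern.** The cut-off is a fixed time, and the intervention adds a step that may affect when treatment starts. If some physicians in the modified arm treat ASB later rather than not at all, the day-2 score records those specimens as successes. No later measurement would show otherwise.

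The hypothesis in the Background is that modified reporting will reduce treatment of ASB. The Implications section looks to fewer complications such as *Clostridium difficile* diarrhea, less resistance and lower cost. All of these depend on antibiotics not being given, and a postponed course brings none of them. The interim rule under Data monitoring uses the same primary outcome, so a significant day-2 difference at about half recruitment would end the trial without this question having been examined.

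**Working it through.** **The plan's own figure.** The Sample size section gives 2N = 90 from 29/55 (52.7%) against 44/55 (80.0%), with 5% type 1 and 20% type 2 error. The two-sided pooled formula is

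n = [1.96 × √(2 × 0.6636 × 0.3364) + 0.8416 × √(0.5273 × 0.4727 + 0.80 × 0.20)]² / 0.2727² = 45.9.

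That is 46 per arm, or 92 in total, within two patients of the stated figure, which is not in dispute here. The planned difference of 27.3 points is the yardstick for what follows.

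**How each case is scored at day 2**

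| True course | Day-2 score | Effect on that arm |
|---|---|---|
| ASB, never treated | appropriate | correct |
| ASB, first treated day 3 or later | appropriate | flatters the arm |
| UTI, treated by day 2 | appropriate | correct |
| UTI, first treated day 3 or later | inappropriate | penalises the arm |

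The two late-start rows pull in opposite directions, so the net effect depends on the case mix.

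**Inputs for an illustration.** All come from the earlier trial as described in the Background, since the protocol gives no long-term-care rates:
- ASB share a = 76/110 = 0.691, so UTI share = 0.309.
- Standard-arm appropriateness p = 29/55 = 0.527.
- tA and tU are the proportions of ASB and UTI eventually treated.

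The documents do not give s, the share of modified-arm treatments that start after day 2. I assume 10%, 20% and 40%, and that the modified report prevents no treatment at all.

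**Equal delay in ASB and UTI.** Net spurious gain = s × (a × tA − (1 − a) × tU). Because p = a × (1 − tA) + (1 − a) × tU, the bracket equals a − p = 0.691 − 0.527 = 0.164, whatever the UTI treatment rate.

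**Delay in ASB only.** Spurious gain = s × a × tA, with tA = [a + (1 − a) × tU − p] / a. For tU = 0.80, tA = 0.595; for tU = 1.00, tA = 0.684. So a × tA runs from 0.411 to 0.473.

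The chance of a significant result is for a two-sided 5% test with 50 per arm and no true effect on eventual treatment. It uses the same normal approximation, from a base of 52.7%.

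| Share delayed | Equal delay: net gain | Chance of significance | ASB-only delay: gain | Chance of significance |
|---|---|---|---|---|
| 10% | 1.6 points | 5% | 4.1–4.7 points | 7–8% |
| 20% | 3.3 points | 6% | 8.2–9.5 points | 13–16% |
| 40% | 6.5 points | 10% | 16.4–18.9 points | 39–50% |

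**When the sign reverses.** Under equal delay the net gain is s × (a − p), which is negative once p exceeds a. For example, with 30% of ASB and 90% of UTI treated, p = 0.691 × 0.70 + 0.309 × 0.90 = 0.762. The net is then 0.691 × 0.30 − 0.309 × 0.90 = −0.071 per unit of delay, and the cut-off works against the modified arm.

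**The case against.** The strongest reply is that nothing shows treatment moving past day 2. The laboratory can be telephoned by day and reached through an on-call technologist at night, a call is a small step within a two-day window, and a physician may treat without calling. The timeline itself treats day 2 as the point by which the treatment decision has been made. This stands. A reader might infer that the intervention itself pushes treatment beyond the cut-off; the documents show only that it could, and that the plan would not detect it.

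A second reply is that late UTI treatment offsets late ASB treatment. This also stands. A reader might take the ASB-only figures as the expected bias in favour of modified reporting. They are an upper case that requires no UTI treatment to be delayed, although the modified report directs the physician to call when UTI is suspected.

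A third reply is that calls are counted, and that specimens with a requested complete report are analysed for appropriateness. This helps in part: delay from waiting on a call can arise only among callers. Neither analysis dates the antibiotic start, and the subgroup is scored on the same outcome.

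A reader might also infer a departure from the earlier trial, because the protocol calls its design identical and the Background says of that trial that "Patients were followed for seven days, and physician treatment decisions were observed". That trial enrolled acute-care inpatients, and the Background does not say that appropriateness was scored through day 7; the seven days may describe safety follow-up. No departure can be asserted.

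Finally, the data collection form is attached to the protocol but not in the text available, so it may already hold antibiotic dates. The outcome and analysis sections would still make no use of them.

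**Conclusion.** The point holds as a gap in what the trial can conclude. Day-2 scoring cannot distinguish avoided from delayed treatment, and the hypothesis and stated implications concern avoidance. It does not show that the day-2 result will be biased, or in which direction.

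At the earlier trial's rates, and assuming no treatment is prevented, equal delay of 10% to 40% gives a net spurious gain of about 1.6 to 6.5 points. ASB-only delay over the same range gives about 4 to 19 points. Both compare with a planned difference of 27.3 points. The delay shares are assumptions, and the mix of ASB and UTI in long-term care may differ enough to change the sign.

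A reader might go further and say that a benefit seen at day 2 but not at day 7 must be reported as delay. That is too strong: with about 50 per arm, chance or newly arising infections could erase a day-2 difference. This is a cheap improvement, not a reason to replace the primary outcome.

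**What to change.** Keep the day-2 primary outcome unchanged, and add the following for both arms.

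1. Record the start date and indication of any antibiotic through day 7, from the health records already accessed and at the day-7 data collection already planned. That collection is now described only as a safety assessment, so its scope would need to be widened in the text.
2. Pre-specify a supporting analysis of appropriateness with treatment for the index culture counted through day 7. Report it beside the day-2 result, overall and separately for ASB and UTI, since the two late-start effects oppose each other.
3. Check starts after day 2 for a new diagnosis against the protocol's own UTI criteria. Where those are met, do not count the start as treatment of the index ASB. The prescriber's stated indication alone is not enough for this.
4. State that any claim of avoided ASB treatment will be interpreted in light of both results, without a mandatory decision rule.

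The cost is one or two case report form fields, some judgement about indication, and one extra analysis. No additional patients or visits are needed.

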Physician consent requirement will be requested to be waived because the intervention poses no more than minimal risk to participants. Patient consent requirement will be requested to be waived because physicians were the research subjects. A letter will be sent to all inpatient physicians informing them about the study prior to recruitment, and a debrief meeting, offering an opportunity to withdraw physician participation, will be provided.

The benefit of this study to patients includes a reduction in adverse events caused by inappropriate antibiotic treatment. The risk to patients includes possible untreated UTI. The benefit to physicians includes education toward appropriate treatment of ASB. The risk to physicians includes additional effort to access laboratory results for UTI.

Protocol amendments

Protocol amendments will be submitted to the ethics committee and trial registry and informed to investigators.

Consent or assent

Not applicable.

Confidentiality

Identification of patients will be required during data collection, but will be removed from trial dataset before analysis. No identifiers will be included in reporting of results.

Declaration of interests

The investigators and sponsor hold no financial interests in the trial.

Access to data

The trial dataset and protocol will be accessible to the investigators during the trial, and made publically available after the analysis is completed.

Ancillary and post-trial care

There will be no post-trial care provided.

Dissemination policy

Investigators will communicate trial results via unrestricted publication. All investigators are eligible for authorship, according to contribution.

Biological specimens

There will be no collection, testing or storage of biological specimens for genetic or molecular analysis.

Budget

The only expense of the project will be the graduate student to collect the data, perform the analysis and write the manuscript.

Implications

A reduction in inappropriate antibiotic treatment may reduce complications of treatment such as diarrhea due to *Clostridium difficile*, selection of bacteria towards drug resistance, and cost of treatment. If the intervention is determined to be safe, it may be considered for implementation in routine laboratory practice. The results will generalize to adult inpatients in Canada and around the world.

References

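### Adverse events are collected to day 30, but the only adverse-event outcome stops at day 7 and no analysis is assigned to events on days 8 to 30

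*Combined protocol and SAP*

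**What the plan says.** The Outcomes section lists three primary safety outcomes: "Mortality rate over thirty days from positive urine culture", "Bacteremia rate over thirty days from positive urine culture" and "Adverse event rate over seven days from positive urine culture". Two run to day 30 and the third to day 7.

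The Participant timeline has a row for "Adverse Events" marked at three post-allocation visits, which read as days 2, 7 and 30. The bacteremia and mortality rows carry the same marks. Harms says it in words: "Adverse events will be collected by the investigators at day 2, day 7 and day 30". Data collection methods adds that family doctors will be telephoned about patients discharged before day 30.

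Elsewhere the plan describes safety more narrowly. The research question under Objectives asks for less inappropriate therapy "without an increase in bacteremia or death over 30 days". The Methods section on participants, interventions and outcomes states: "The primary safety outcome is rate of bacteremia and death". Neither mentions adverse events.

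Statistical methods describes the comparison of appropriate treatment and says nothing about how any safety outcome is analysed.

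**The concern.** The trial plans to gather adverse events for 30 days and then to summarise only the first 7. An analyst who follows Outcomes to the letter would hold data on days 8 to 30 with no instruction for using them. The alternatives are to report everything collected or to choose a window once the results are visible. The Blinding section says the analyst knows the allocation, so it is better not to leave that choice open.

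The adverse-event rate matters because of what the other two safety outcomes cannot see. Under Research ethics approval, the plan states: "The benefit of this study to patients includes a reduction in adverse events caused by inappropriate antibiotic treatment". It gives the risk to patients as UTI that may go untreated. Implications offers *C. difficile* diarrhea as an example of a treatment complication. Deaths and positive blood cultures do not register antibiotic side effects, or an untreated UTI that never reaches the bloodstream. Of the listed outcomes only the adverse-event rate can, and it has the shortest window of the three. Implications also says that a finding of safety could lead to routine use, so the safety summary would inform a real decision.

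**Working it through.** **1. The plan's own figure.** The documents give no expected adverse-event rate, so there is nothing to reproduce on this outcome. The only computed design figure is the total of 90 for the efficacy outcome. With 29/55 and 44/55, two-sided 5% error and 80% power, the unpooled formula gives

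n per arm = (1.960 + 0.842)² × (0.527 × 0.473 + 0.800 × 0.200) / 0.273² ≈ 43.2, rounded up to 44, or 88 in total.

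The pooled version gives 46 per arm, or 92. Both are within 2 of the stated 90. Adverse events do not enter this calculation, so nothing below changes it.

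**2. Windows side by side.**

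| Outcome | Collected at (Participant timeline; Harms for adverse events) | Outcome window (Outcomes) | Named as safety outcome in Methods |
|---|---|---|---|
| Death | days 2, 7, 30 | 30 days | yes |
| Bacteremia | days 2, 7, 30 | 30 days | yes |
| Adverse events | days 2, 7, 30 | 7 days | no |

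The Harms sentence establishes day-30 collection of adverse events on its own, so the reading does not depend on how the timeline table was extracted.

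**3. Follow-up outside the outcome.** 30 − 7 = 23 days; 23/30 = 77% outside and 7/30 = 23% inside. This is a share of calendar time, not of events.

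**4. What that could mean in patients (assumptions, for scale only).** Suppose the hazard of a first adverse event is constant over 30 days and the 30-day risk is R. The 7-day risk is then 1 − (1 − R)^(7/30), and the share of affected patients not counted is (R − 7-day risk)/R.

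| Assumed 30-day risk R | 7-day risk | Share not counted |
|---|---|---|
| 5% | 1.2% | 76% |
| 10% | 2.4% | 76% |
| 20% | 5.1% | 75% |
| 30% | 8.0% | 73% |
| 50% | 14.9% | 70% |

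For example, with about 50 patients per arm and R = 20%, about 10 per arm would have an event by day 30 (50 × 0.20) and about 2.5 by day 7 (50 × 0.051). If instead half of all events fell in the first week, 50% would go uncounted, and stronger early clustering would reduce that further. The documents do not say which pattern to expect.

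**The case against.** The strongest reply is that an outcome window shorter than the surveillance period is not in itself an error. A plan may watch for harm to day 30 and compare arms at day 7. The previous trial followed patients for seven days, and this one sets out to repeat its design, so the window may be deliberate. In a frail population, a longer window may also add events unrelated to a single laboratory report. All of this stands as a reason not to call seven days wrong. It does not answer the narrower point: the plan gives no reason for seven days and does not say what happens to later events. Serious events go to the ethics committee within 24 hours, but that is notification, not a comparison of arms.

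A reader might infer three stronger things that the documents do not support.

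- *The 30-day safety question goes unanswered.* It does not. That question names bacteremia and death, and both have 30-day outcomes.
- *Events are certainly dropped from a primary safety outcome.* That depends on which section governs. Outcomes lists adverse events as primary; Methods does not.
- *A 7-day rate understates the difference between arms.* A shorter window counts no more events than a longer one, but the difference between arms may shrink, grow or stay the same. With no rate or timing in the documents, this cannot be shown.

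**Conclusion.** The mismatch is real and minor. As written, 23 of 30 days (77%) of collected adverse-event follow-up fall outside the only outcome that can capture harms other than bacteremia and death, and no other analysis is assigned to them. This assumes that the day-30 assessment is meant to pick up events since day 7, which is the natural reading of Harms.

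The number of events affected is unknown. The 70% to 76% range rests on an assumed constant hazard and assumed 30-day risks of 5% to 50%; early clustering would lower it. Nothing here touches the efficacy comparison, the sample size, or the bacteremia and death outcomes. The documents do not establish that thirty days must replace seven. They do support reporting both, and resolving the disagreement between Methods and Outcomes over whether adverse events are a primary safety outcome.

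**What to change.** In Outcomes, add the adverse-event rate over thirty days from positive urine culture, by arm, next to the 7-day rate and on the same counting rule. Keep the 7-day rate for comparison with the previous trial. Add a line to Statistical methods saying that both rates will be reported, so that the choice of window is made before the data are seen.

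In the same edit, reconcile Methods with Outcomes by stating in both places whether adverse events are a primary safety outcome or a further safety outcome alongside bacteremia and death.

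The cost is two or three sentences of protocol text and one extra row of output. No new data collection is needed, because the day-30 assessment is already planned. The drawback is that the 30-day rate may contain more background events unrelated to the intervention; showing the two windows together lets the reader judge that.

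### The primary test is named two ways and no analysis set is labelled primary; more importantly, per-protocol exclusions and chart data can be settled with the arm visible, so the 5% error rate is not protected

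*Combined protocol and SAP*

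**What the plan says.** **Test.** The last paragraph of Sample size states: "The statistical test to be used is a comparison of proportions between two groups (T test, two-sided analysis". Statistical methods states: "The proportion of appropriate treatment will be compared using two-sided Pearson chi squared test".

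**Analysis set.** Sample size commits to ITT on everyone randomised and gives a reason. Statistical methods defines ITT as specimens that were both randomised and reported on, a slightly different set, and adds: "Specimens inappropriately included will be excluded from the Per-protocol (PP) analysis". Neither set is called primary. No one is named to decide these exclusions and no time is set for deciding them. Data monitoring ties the interim stop to significance of the primary outcome without naming a set.

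**Who sees the arm.** Blinding says investigators are blinded, but also: "Data analyst will not be blinded to assignment". No reason is given. Budget says: "The only expense of the project will be the graduate student to collect the data, perform the analysis and write the manuscript". Data management has a graduate student enter the data. Access to data says: "The trial dataset and protocol will be accessible to the investigators during the trial".

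**Safeguards.** A physician investigator makes the diagnosis (Data collection methods). After entry, a second investigator reviews the data and the dataset is locked before analysis (Data management). There is no auditing and no data monitoring committee.

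**The concern.** Two tests are named for one outcome, so one sentence must be wrong. Two sets are described and the deciding one has to be inferred.

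The larger problem is the combination of roles. The primary outcome is an appropriateness judgement drawn from charts. The person who gathers and enters that material also analyses it by arm. At the interim look this person would see results by arm and then go on collecting outcomes. Nothing requires the per-protocol exclusions, or the chart-derived data, to be settled before the arm is known. Both the final claim and the interim stop depend on significance of this analysis, so its nominal error rate holds only if no decision was influenced by the arm or the result. The plan contains little that would let a reader confirm that.

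**Working it through.** **Inputs from the protocol.** Rates of 29/55 and 44/55, 2N = 90 raised to 100, 1:1 allocation (Sample size; Trial design). Error rates: "Accepting a risk of type 1 error of five percent, and a risk of type 2 error of twenty percent". One interim look at about half of recruitment with no adjustment stated (Data monitoring).

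**Assumed.** The share e of specimens dropped from the per-protocol set. The protocol gives no figure; 5% to 20% is used.

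**1. The plan's own sample size.** Pooled rate (0.5273 + 0.8000)/2 = 0.6636.

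n per arm = [1.96·√(2·0.6636·0.3364) + 0.842·√(0.5273·0.4727 + 0.80·0.20)]² / 0.2727² = (1.310 + 0.538)² / 0.0744 = 45.9, so 46 per arm and 92 in total. This is within 2 of the stated 90.

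**2. Does the choice of test matter?**
- On the earlier trial's counts, chi-squared gives z = 3.03, p = 0.0025; the pooled t test gives t = 3.13 on 108 df, p = 0.0022.
- Exact enumeration under no effect (total 90 or 100, including mildly unequal arms, common rates 0.40 to 0.80) puts the two tests on opposite sides of 0.05 with probability 0 to 0.6%. An example is 30/45 vs 38/45: p = 0.0497 and 0.0505.
- In every case run, taking whichever test was significant gave the same error rate as chi-squared alone (for example 5.65% for each at 50 per arm, rate 0.527).

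**3. Does the choice of set matter?** If a share e is excluded at random, the ITT and per-protocol z-statistics have correlation √(1 − e). The chance that at least one is significant under no effect is 1 − P(|Z₁| ≤ 1.96 and |Z₂| ≤ 1.96).

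| e (assumed) | correlation | error if the better set is reported |
|---|---|---|
| 2% | 0.990 | 5.7% |
| 5% | 0.975 | 6.0% |
| 10% | 0.949 | 6.5% |
| 20% | 0.894 | 7.1% |

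Binomial simulation at 50 per arm gave 6.0% to 7.0% for e of 5% to 10%, against 4.9% to 5.8% for ITT alone in the same runs.

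**4. Exclusions that follow arm and outcome.** This is an illustration, not a prediction. 24/45 vs 32/45: pooled 56/90 = 0.622, difference 0.178, SE 0.102, z = 1.74, p = 0.082. Drop two inappropriately treated specimens from the modified arm, giving 32/43: pooled 56/88 = 0.636, difference 0.211, SE 0.103, z = 2.06, p = 0.040. Two exclusions move the result across 0.05.

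**5. The interim look.** With one test on one set and two unadjusted looks at 50% and 100%, the correlation is √0.5 = 0.707 and the same formula gives 8.3%. Simulation at 25 then 50 per arm gave 8.7% to 10.1%.

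**The case against.** The strongest reply is that this is loose wording. Statistical methods is the section that should govern, and it names chi-squared. Sample size attaches ITT to the comparison, the trial is a superiority trial, and per-protocol appears only after ITT. The exclusion criteria (not a long-term care specimen, pregnancy, antibiotics at collection, known low neutrophils) are largely checkable facts that predate the report. A physician investigator makes the diagnosis, and the dataset is locked before analysis.

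Most of this stands, and it rules out two stronger readings. A reader might infer that naming two tests inflates the error rate; step 2 shows that it does not. A reader might also infer that the plan lets the analyst choose the test or the set; no section says so, and the rates in step 3 arise only if the set is picked on its result. Nor does the roughly 40% exclusion quoted in Sample size support a larger figure, since it describes eligibility exclusions in another trial, not losses from a per-protocol set.

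What does not stand is the reliance on the lock. It follows completed data entry, and none is described for the interim look. The criteria are factual, but antibiotic use at collection may come to light only at chart review, after the report has gone out. Access to data does not say whether the investigators' dataset carries allocation, but nothing keeps it out.

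Masking also has limits. Charts may show the modified report, and call records point to that arm.

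**Conclusion.** The concern holds as a weakness in how the analysis is protected; it does not show that the error rate is wrong. The conflict between tests and the missing label for the primary set are wording faults with negligible numerical effect. The substantive point is that exclusions and chart-derived data can be settled with the arm visible. If that led to a result-driven choice of set, the error would be about 6.0% to 7.1%, resting on the assumed 5% to 20% random exclusion. Exclusions related to arm and outcome could do more, by an amount the documents do not allow one to estimate. The unadjusted interim look is a larger and separate source, at about 8.3% even with test and set fixed. The planned sample size is unaffected.

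**What to change.** 1. Delete the T test from Sample size.
2. Name the ITT Pearson chi-squared comparison as primary at both the interim and final looks, with a single definition of ITT. Make per-protocol a sensitivity analysis.
3. Keep the allocation column out of the working dataset open to the student and the investigators.
4. Settle per-protocol exclusions against the listed exclusion criteria before allocation is merged: on a frozen extract at the interim, and on the locked dataset at the end.
5. Run the primary analysis on arms coded A and B. Hold call records back until that result is fixed, then analyse the call outcome and the caller subgroup.
6. Deal with the interim significance level as its own amendment. For scale, two equally strict looks would each need nominal p < 0.0294.

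Items 1 to 5 cost protocol wording, one withheld column and one extra data freeze at the interim. Sample size does not change. Masking will be incomplete where the chart shows the modified report, and the protocol should say so.
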